### **Intake Assessment**

All prospective participants will complete a formal assessment at intake; participants will receive \$25 for completing the assessment. The screening will take no more than 2 hours. Prior to completing the intake assessment, the prospective participant will read through and sign the consent form; the consent form will contain information about the intake assessment and its procedures, along with the study procedures. During the intake, questionnaires will be completed using pen and paper, then will be uploaded onto the computer and into a secure web platform, REDCap. The assessment battery will include questionnaires that assess the following six areas: (1) sociodemographic, (2) substance use history, (3) substance use follow-back, (4) substance craving, (5) demand for substances, and (6) decision making. The first 3 areas will be assessed using the WA state syringe exchange survey and Treatment Effectiveness Assessment. Substance craving will be assessed using the three-item craving scale. Demand for substances will be assessed using the simulated substance purchase task. Decision making will be assessed using the monetary choice questionnaire. For additional detail about each measure, see each respective questionnaire. Participants will receive \$25 for their time and participation in completing the intake assessment.

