### **Data Collection**

The primary dependent variable is stimulant-free urine samples; all samples will be assessed using point-of-care test conducted at the center. Urine specimens will be collected for all participants at least once weekly throughout the study. Urine specimens are disposed of following recording of the result, thus, no samples are stored. Participants in the health education condition will receive \$10 for providing each urine sample (2x per week). Urine samples will be collected for participants in the financial incentives condition twice weekly for all 12 weeks of the intervention for which they can earn the incentives stated above by providing a negative urine sample. Participants in both conditions will also complete the questionnaires for decision making, demand for substances, craving, and treatment effectiveness at three additional times after baseline, at weeks 4, 8, and 12. Data for the questionnaires will be completed using pen and paper, then will be uploaded onto the computer and into REDCap. All participants will be compensated \$10 per assessment independent of substance use status to ensure high compliance.

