Participant baseline demographics and characteristics will be compared between treatment conditions (Health Education vs. health Education plus Incentives for Abstinence) using Chi Square Tests of Independence or Fisher's Exact Tests for categorical variables and Wilcoxon Rank Sum Tests or Two-Sample T-tests for continuous variables, depending on the distributions of the variables. If a specific characteristic differs significantly between treatment conditions and is predictive of the outcome, it will be considered as a potential covariate in subsequent analyses. The primary outcome to be analyzed will be point-prevalence stimulant abstinence, which will be determined by percentage of negative urine samples for stimulants using a point-of-care test. Analyses of treatment condition effect on point-prevalence stimulant abstinence will adhere to an intent-to-treat approach whereby all participants randomized to each treatment condition will be included in the analyses independent of early dropout, noncompliance, etc. Point-prevalence abstinence rates will be compared between treatment conditions at individual timepoints using Chi Square Tests of Independence. Comparisons of point-prevalence abstinence rates between treatment conditions across all assessments will be analyzed using mixed model repeated measures for categorical data based on generalized estimating equations (GEE) using a logistic link function. Comparisons of predictors of abstinence that are continuous outcomes and continuous outcomes based on survey responses between treatment conditions across all assessments will be analyzed using mixed model repeated measures analyses of variance. Comparisons of predictors of abstinence that are categorical outcomes and categorical outcomes based on survey responses between treatment conditions across all assessments will be analyzed using mixed model repeated measures for categorical data based on generalized estimating equations (GEE) using a logistic link function.

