Because this is an exploratory pilot study evaluating the potential efficacy, feasibility, and acceptability of a contingency management intervention for stimulant use within a syringe exchange program, we are proposing a small, initial pilot study of 40 participants. Data from a previous meta-analysis study (Bolívar et al., 2021), which examined the CM treatment effects on abstinence from psychomotor stimulant use found a mean effect size for treatment effect on abstinence from psychomotor stimulant of Cohen's  $d = 0.70$ . However, among studies included in this analysis, the minimum effect size which was for the outcome of point-prevalence stimulant abstinence was Cohen's  $d = 0.51$  ([name] et al., 2002; doi:10.1001/archpsyc.59.9.817). Using this "medium" effect size for sample size calculation, in order to detect a statistically significant difference in point-prevalence stimulant abstinence between treatment conditions with 80% power, with 2-sided significance level alpha of 0.05, a total sample size of 88 participants would be required. However, because this is an initial pilot study looking to assess feasibility and potential efficacy, we expect to observe discernable differences between the two conditions with a sample size of 40. The goal is to conduct a pilot study where the data could then be used to inform a larger, fully powered randomized control trial.

**Risks/Benefits:** Describe any potential or known risks. This includes physical, psychological, social, legal or other risks. Estimate the probability that given risk may occur, its severity and potential reversibility. If the study involves a placebo or washout period, the risks related to these must be addressed in both the protocol and consent. Describe the planned procedures for protecting against or minimizing potential risks and assess their likely effectiveness. Where appropriate, discuss plans for ensuring necessary medical or professional intervention in the event of adverse effects to the subjects. Discuss the potential benefits of the research to the subjects and others. Discuss why the risks to the subjects are reasonable in relation to the anticipated benefits to subjects and others. Discuss the importance of the knowledge gained or to be gained as a result of the proposed research and why the risks are reasonable in relation to the knowledge that reasonably may result. If there are no benefits state so.

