Participants are free to withdraw from the study at any time and for any reason while they are completing the study. Participants may be withdrawn if the PIs determine it is not advisable that they continue on in the study. Regarding data analysis, we will adhere to an intent-to-treat approach (Armitage, 1983) wherein all participants randomized to the study conditions will be included in the analyses independent of early dropout, or noncompliance.

**Sources of Materials:** Identify sources of research material obtained from individually identifiable human subjects in the form of specimens, records or data. Indicate whether the material or data will be obtained specifically for research purposes or whether use will be made of existing specimens, records or data.

All data collected will be for research purposes only. This study will include individuals 18 years and older who participate in services provided by Safe Recovery at the Howard Center in Burlington, VT. The data collected will include both answers to the questionnaires described above and urine specimens which will be tested for psychomotor stimulants. Thus, the sources of materials include:

- Questions on sociodemographic, substance use history, and substance use follow-back
- Questions on demand for substances, decision making, and substance craving
- Urine samples to be tested for recent stimulant use

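### The plan does not say how the intake score enters the continuous questionnaire analyses, or which contrast is the treatment effect; precision in these secondary outcomes may be lost

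*Combined protocol and SAP*

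**What the plan says.** Intake Assessment lists the baseline instruments; for example, "Substance craving will be assessed using the three-item craving scale". Data Collection then has both arms repeat the questionnaires for "decision making, demand for substances, craving, and treatment effectiveness at three additional times after baseline, at weeks 4, 8, and 12".

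For these scores Statistical Considerations states that "continuous outcomes based on survey responses between treatment conditions across all assessments will be analyzed using mixed model repeated measures analyses of variance". It names no intake-score term and no contrast, and does not say whether intake counts among the assessments analysed.

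The section's only covariate rule depends on the data: "If a specific characteristic differs significantly between treatment conditions and is predictive of the outcome, it will be considered as a potential covariate". The baseline comparisons behind it are "Wilcoxon Rank Sum Tests or Two-Sample T-tests for continuous variables, depending on the distributions of the variables". No significance level is given for them. The two-sided 0.05 in the same section belongs to the sample-size calculation for abstinence.

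On purpose, the section says: "The goal is to conduct a pilot study where the data could then be used to inform a larger, fully powered randomized control trial". Withdrawal Procedures adds that "all participants randomized to the study conditions will be included in the analyses independent of early dropout, or noncompliance".

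**The concern.** An intake score on the same scale usually predicts the later score, and here it is already collected. Using it well narrows the interval for the arm difference at no cost in data, which is worth having with 40 participants.

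The wording leaves several analyses open:

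- **Weeks 4, 8 and 12 as responses, average arm difference.** Intake can enter only through the significance rule, which is rarely met under randomisation.
- **Weeks 4, 8 and 12 as responses, arm-by-week test.** An effect that is constant over those weeks is not detected.
- **Intake as a fourth response, arm-by-time contrast against intake.** This behaves like a change score.
- **Intake as a fourth response, arm main effect over all four occasions.** This averages in a time point at which no effect can exist.

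At stake are the width of the intervals for these secondary outcomes and the freedom to choose among analyses once the data are seen.

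**Working it through.** The plan gives no figure on this point to reproduce; its sample-size calculation concerns abstinence only.

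**Inputs.** From the documents: 40 participants in total, random assignment to two arms, and scores at intake and weeks 4, 8 and 12. Assumed: 20 per arm (the ratio is not stated), SD 1 at every occasion, within-person correlation r = 0.3, 0.5 or 0.7, complete data, and 0.05 two-sided for the baseline tests.

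**Step 1: the covariate rule.** Intake precedes the intervention and arms are randomised, so any intake difference is chance. Then P(admitted) = P(significant and predictive) ≤ P(significant) = the level of the test. In 40,000 simulated trials per setting with no treatment effect, both conditions were met in 4.0/4.9/5.1% for r = 0.3/0.5/0.7. The ceiling is whatever level is used, and a score that passes is still only to be considered.

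**Step 2: precision.** Let M be a participant's mean over weeks 4, 8 and 12, and B the intake score.

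- Compound symmetry: Var(M) = (1 + 2r)/3, Cov(M,B) = r.
- AR(1), r between adjacent occasions: Var(M) = (3 + 4r + 2r²)/9, Cov(M,B) = (r + r² + r³)/3.
- Variance per participant, V: unadjusted Var(M); change Var(M) + 1 − 2Cov; intake-adjusted Var(M) − Cov².
- 95% half-width = t × √(2V/20), with t = 2.024 (38 df), or 2.026 (37 df) when adjusted.
- The adjusted half-width is multiplied by √(1 + 1/36) = 1.014, the average cost of estimating the intake slope when arms differ by chance at intake.

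Worked case, compound symmetry, r = 0.5:

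- Unadjusted: V = 2/3, so 2.024 × √(0.1 × 0.667) = 0.523.
- Change: V = 0.667 + 1 − 1 = 0.667, so 0.523.
- Adjusted: V = 0.667 − 0.25 = 0.417, so 2.026 × √(0.1 × 0.417) × 1.014 = 0.419.
- Gain over either: 1 − 0.419/0.523 = 20%.

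Half-widths in SD units:

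| Structure | r | Unadjusted | Change | Adjusted | Narrower than unadjusted | Narrower than change |
|---|---|---|---|---|---|---|
| Compound symmetry | 0.3 | 0.468 | 0.618 | 0.433 | 7.5% | 30% |
| | 0.5 | 0.523 | 0.523 | 0.419 | 20% | 20% |
| | 0.7 | 0.573 | 0.405 | 0.362 | 37% | 11% |
| AR(1) | 0.3 | 0.447 | 0.704 | 0.444 | 0.6% | 37% |
| | 0.5 | 0.500 | 0.649 | 0.471 | 6% | 27% |
| | 0.7 | 0.556 | 0.547 | 0.456 | 18% | 17% |

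Simulation of complete data gave the same gains to rounding.

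**Step 3: the other contrasts.** Take a constant effect δ at weeks 4, 8 and 12, and none at intake. The equally weighted arm main effect over four occasions estimates (0 + δ + δ + δ)/4 = 3δ/4. An arm-by-week test restricted to weeks 4 to 12 compares δ with δ, so it looks for a difference of zero.

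**The case against.** The strongest reply is that the model may already use intake. The protocol treats intake as an assessment and the later ones as additional, so an analysis over all assessments can naturally include it as a response. The covariate rule, introduced for baseline characteristics, is then not the gateway, and the 5% figure is beside the point. This stands: the 5% applies only if weeks 4 to 12 are the responses. It does not settle the matter, because a contrast against intake is still wider than the adjusted one in every case tabulated, and the text does not say that this contrast is meant.

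It is also true that the gain can be negligible (0.6% over no adjustment under AR(1) with r = 0.3), that the outcomes are secondary, and that no sample size or decision rests on them. The plan does not tie questionnaire interval widths to the design of the larger trial. These points lower the priority.

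A reader might go further and infer bias or false positives. The documents do not support that. With random assignment the unadjusted and change comparisons are valid, and applying the covariate rule gave a simulated type I error of 4.6/4.1/3.1%, at or below nominal.

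A reader might also extend the remedy to the GEE for categorical survey outcomes. That does not follow. Under a logit link, adding intake changes the odds ratio being estimated: with an assumed latent effect of 0.5, the median log odds ratio moved from about 0.81/0.85/0.81 to 0.84/0.99/1.08 for r = 0.3/0.5/0.7. Its interval did not narrow.

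**Conclusion.** The gap is real but small in consequence. For continuous questionnaires measured at intake and follow-up, the plan fixes neither the role of the intake score nor the treatment contrast. No reading that the text states secures the available precision, although a mixed model with a common intake mean across arms would.

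The gain from adjustment runs from about 1% to 37% of interval width, depending on the correlation structure and on which analysis it replaces. Among the cases examined, where it is small against one alternative it is larger against the other. These figures rest on assumed correlations, equal SDs, 20 per arm and complete data; none of these is given in the documents. The 5% admission rate rests on an assumed test level.

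The primary abstinence analysis is unaffected. So is the acceptability questionnaire, which is given once at or shortly after week 12 (Examining Intervention Acceptability) and has no intake score. This is an optional, low-priority improvement.

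**What to change.** For each continuous questionnaire measured at both intake and follow-up, prespecify adjustment for the intake score of the same measure, whatever any baseline significance test shows. Either form serves:

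- **(a)** Weeks 4, 8 and 12 as outcomes, with intake score, arm, week and arm-by-week as terms. Report by arm how many participants are left out for lack of a follow-up score.
- **(b)** A constrained-baseline mixed model: intake as a response with one mean common to both arms, and arm-by-week effects at weeks 4, 8 and 12.

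Name the treatment contrast as the arm difference averaged over weeks 4 to 12, and give the week 12 difference as well, each with a 95% confidence interval. Leave the GEE for categorical survey outcomes as it is.

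The cost is two or three sentences, with no new data or participants. If 20% had no follow-up questionnaire (assumed), form (a) would leave out 8 of 40. Form (b) keeps them, which sits better with the intent-to-treat statement. Its precision advantage is slight: simulated half-widths were 0.478/0.464/0.401 against 0.487/0.475/0.408 for form (a), about 2%.

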### **Intervention Conditions**

Participants will be randomly assigned to one of two intervention conditions. These sessions will be administered by one of the following study team members: Howard Center research assistants, UVM research assistants helping with the project, or Drs. [name] and [name].

**Health Education Condition.** The Health Education condition is based on a previous intervention used as a control in a number of other studies (Mooney et al, 2013). Sessions consist of an educational program addressing a variety of health, wellness, and lifestyle topics adapted from a previously implemented wellness manual. One education topic will be discussed each day. The 12 daily educational topics will include: (1) stress relief, (2) nutrition, (3) hepatitis prevention, (4) HIV prevention, (5) sleep hygiene, (6) health screening, (7) meditation, (8) home emergencies, (9) healthy relationships, (10) common medical problems of people who use drugs, (11) strategies to reduce anxiety, depression and other negative moods, and (12) self-defense. Participants in this condition will be scheduled for two clinic visits per week for 12 weeks. Thus, the health education on the 12 topics listed above will be provided in addition to the services provided to all individuals in the Howard Center Safe Recovery program. At one session each week, the individual will meet with a study team member listed above who will review a topic handout with the participant. We anticipate these sessions will take approximately 10-15 minutes.

**Health Education plus Incentives for Abstinence.** Participants in the experimental condition will have the opportunity to earn financial incentives for abstaining from stimulant use, in addition to receiving the same health education as the control condition. Monitoring of stimulant use will occur through twice-weekly urinalysis during the 12 weeks of the intervention. Specimens will be screened for stimulant use using a 10-panel point-of-care test taken at the center. The financial incentives will be contingent on negative samples for stimulants which include cocaine, methamphetamine, and amphetamine. The incentive amount will start at \$25 and increase for each subsequent stimulant-negative urine sample, up to \$65 per sample. Only tests where the display indicates negative samples will result in participants earning reinforcement. The incentive amount

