**\*\*If genetic information is being collected, GINA language must be added to the consent form.**

\*Deception typically involves withholding information from the potential subject and would require an alteration to the consent process.

**Statistical Considerations:** Delineate the precise outcomes to be measured and analyzed. Describe how these results will be measured and statistically analyzed. Delineate methods used to estimate the required number of subjects. Describe power calculations if the study involves comparisons. Perform this analysis on each of the primary and secondary objectives, if possible.

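### The 88 participants said to give 80% power at d = 0.51 do not follow from those inputs; a single-timepoint comparison needs about 120 to 129

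*Combined protocol and SAP*

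**What the plan says.** All of this is in the Combined protocol and SAP, mostly under Statistical Considerations.

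- **Effect size.** The sample-size paragraph cites a meta-analysis with a mean effect of d = 0.70. It then adopts a smaller value: "the minimum effect size which was for the outcome of point-prevalence stimulant abstinence was" d = 0.51, which it labels medium.
- **Purpose and result.** The calculation is made "in order to detect a statistically significant difference in point-prevalence stimulant abstinence between treatment conditions", and the paragraph concludes that "with 80% power, with 2-sided significance level alpha of 0.05, a total sample size of 88 participants would be required".
- **Actual size.** Enrolment is set at 40 because this is an exploratory pilot meant to inform a later, fully powered trial. The paragraph adds that "we expect to observe discernable differences between the two conditions with a sample size of 40".
- **Analyses.** The preceding paragraph plans two comparisons of the primary outcome. The first is "Point-prevalence abstinence rates will be compared between treatment conditions at individual timepoints using Chi Square Tests of Independence". The second is a GEE analysis with a logistic link: "Comparisons of point-prevalence abstinence rates between treatment conditions across all assessments will be analyzed using mixed model repeated measures for categorical data".
- **Allocation.** Under Intervention Conditions: "Participants will be randomly assigned to one of two intervention conditions". No ratio is given.
- **Form instruction.** The form asks the investigators to "Delineate methods used to estimate the required number of subjects".

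**The concern.** Effect size, significance level, sidedness and power are all stated, so the total can be checked directly, and 88 looks too small for d = 0.51. The paragraph does not say which of the planned analyses produced 88, what abstinence rates were assumed, how d was turned into a difference in proportions, or what allocation was used. A reader cannot trace the figure.

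Two things are at stake. First, 88 is the only number the plan links to 80% power. Anyone who used it to size a single-timepoint comparison at d = 0.51 would have an underpowered trial. Second, 88 makes 40 look like nearly half of a powered study (40/88 = 45%), when it is about a third (40/124 = 32%). That flatters the expectation of seeing a difference at 40.

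**Working it through.** **Inputs.** From the sample-size paragraph: d = 0.51, two-sided alpha 0.05, power 0.80, stated total 88, planned total 40. Assumed: 1:1 allocation (44 or 20 per arm), the ratio that minimises the total, and one timepoint. The normal quantiles are 1.960 and 0.8416; their sum is 2.8016, with square 7.849.

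**1. Trying to reproduce 88 from d = 0.51**

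- *Two means, normal approximation.* n per arm = 2 × 7.849 / 0.51² = 15.698 / 0.2601 = 60.4, so 61 per arm and **122** in total.
- *Two-sample t-test (noncentral t).* 61.33 per arm, so 62 per arm and **124** in total.
- *Chi-square, 1 df, N = 7.849 / w².* If d is the difference over the total SD, w = d/2 = 0.255 and N = 7.849 / 0.06503 = 120.7, so **121**. If d is the difference over the within-arm SD, w = d/√(d² + 4) = 0.247 and N = 128.6, so **129**.
- *Two proportions, pooled variance under the null.* At w = 0.255, n per arm = [1.960√2 + 0.8416√(2 − d²/2)]² / d² = (2.772 + 1.151)² / 0.2601 = 59.2, so 60 per arm and **120** in total. At w = 0.247 the unrounded total is 126.2.
- *Arcsine effect size h = 0.51.* N = 120.7 before rounding.
- *d read as an odds ratio.* OR = exp(0.51 × π/√3) = 2.52. The documents give no control abstinence rate; over an assumed 5% to 50% the pooled two-proportion test gives:

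| Control (assumed) | Treatment | Total N | Power at 88 | Power at 40 |
|---|---|---|---|---|
| 5% | 11.7% | 532 | 20% | 12% |
| 10% | 21.9% | 296 | 33% | 17% |
| 20% | 38.7% | 186 | 49% | 25% |
| 30% | 51.9% | 156 | 55% | 29% |
| 40% | 62.7% | 150 | 57% | 30% |
| 50% | 71.6% | 158 | 55% | 28% |

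No version gives 88. A one-sided test, contrary to the stated alpha, would still need 96 (normal) or 98 (t-test). A continuity correction or an allowance for dropout only raises the total.

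**2. Power at the stated and planned sizes, d = 0.51**

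| Method | Power at 88 | Power at 40 |
|---|---|---|
| t-test | 65.7% | 34.9% |
| Chi-square, w = 0.255 | 66.7% | 36.4% |
| Chi-square, w = 0.247 | 64.0% | 34.6% |
| Two proportions, w = 0.255 | 67.3% | 36.0% |

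**3. What 88 does correspond to**

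- With 44 per arm, 80% power needs d = 2.8016 × √(2/44) = 0.597 (normal) or 0.604 (t-test).
- A 1-df chi-square with w = 0.30 gives N = 7.849 / 0.09 = 87.2, so 88. The conventional medium value on the w scale is 0.30, so the medium label may have been carried from one scale to the other. This is an inference, and the finding does not rest on it. In any case w = 0.30 corresponds to d of 0.60 (as 2w) or 0.63 (as 2w/√(1 − w²)), not 0.51.

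**The case against.** **The primary outcome is measured repeatedly, and the paragraph never says that 88 is for one timepoint.** This is the strongest point. Averaging m repeats with within-person correlation ρ multiplies the required number by [1 + (m − 1)ρ]/m. To bring 60.4 per arm down to 44, the factor must be 0.729. That needs ρ of about 0.59 with 3 repeats or 0.72 with 24; the exact values shift by a few hundredths with the formula used. Such correlations are not extreme, so 88 could be defended this way. The plan, however, gives no correlation, number of repeats or repeated-measures method for the sizing. The point stands only as a route the sponsor may take by stating those inputs.

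**The expectation at 40 has some basis.** The plan cites a mean effect of 0.70, treats 0.51 as the minimum, and does not claim 80% power at 40. That is fair. But even at d = 0.70 the t-test has only 58% power with 20 per arm; 80% power would need d of about 0.91, above both cited effects.

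**A test is named.** The analysis paragraph does name chi-square and GEE. What is missing is which of them lies behind 88.

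**The odds-ratio figures rest on assumed control rates.** They do. The conclusion stands on the t-test and chi-square results without them.

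**The 88 sets nothing in this trial.** Correct: enrolment is 40 on openly stated pilot grounds. This limits the severity but does not make the figure right.

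**Conclusion.** The concern holds. For a single-timepoint comparison with 1:1 allocation, d = 0.51 at two-sided 0.05 and 80% power needs 124 by t-test and 121 to 129 by chi-square, with 120 as the lowest figure found. The stated 88 is therefore about 27% to 32% too small (88/121 = 0.73; 88/129 = 0.68). If d is read as an odds ratio of 2.52, the shortfall is at least 41% (88/150 = 0.59) over the assumed control rates. Power is at most about 67% at 88 and 36% at 40.

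The conclusion is confined to one timepoint; a repeated-measures calculation might support 88, but none is given. The consequence is a published sample size that its own inputs do not deliver, together with an expectation at 40 that lacks a stated power or precision. Enrolment and analyses are unaffected. It should be fixed, but it does not threaten the conduct of the pilot.

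**What to change.** Keep the enrolment of 40 and rewrite the sample-size paragraph.

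1. Name the test, the allocation ratio, and either the two abstinence rates or the rule that converts d into proportions. Compute every figure on that one basis.
2. Either replace 88 (about 124 if d = 0.51 is used with a 1:1 t-test), or keep 88 and justify what yields it: a larger effect (d about 0.60 by t-test), or the correlation and number of repeats for a repeated-measures calculation.
3. Replace the expectation of differences at 40 with the power or the expected 95% confidence-interval width at 40, from the same test and rates.

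Two self-consistent examples, not to be mixed:

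- **A.** d = 0.51, t-test: total 124, power 35% at 40. The interval half-width at 20 per arm is 1.96 × √(1/20 + 1/20 + 0.51²/80) = 0.63 SD.
- **B.** Odds ratio 2.52 with an assumed control abstinence of 20% (20% against 38.7%), two-proportion test: total 186, power 25% at 40. The half-width is 1.96 × √[(0.2 × 0.8 + 0.387 × 0.613)/20] = 0.276, about 28 percentage points.

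The cost is one reworded paragraph, with no extra participants, visits or analyses. The only downside is that the figures become less favourable, or that a larger effect or repeated-measures inputs must be stated and defended.
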